2.3.2 Clinical outcomes

Outcomes, their time of measurement and source are shown in table 1.

[figure not shown]
Outcome	Time point of measurement	Data Source
Return Of Organised Rhythm (ROOR)	2 minutes after delivery of each shock	Defibrillator data downloads
Resulting rhythm (VF/pVT/PEA/asystole)	2 minutes after delivery of each shock	Defibrillator data downloads
Refrillation rate	At any point during out-of-hospital phase	Defibrillator data downloads

Survived event (return of spontaneous circulation (ROSC) at hospital handover)	At hospital handover	Patient status at handover recorded on electronic patient clinical record by ambulance staff
Survival to 30 days and hospital discharge	30 days and hospital discharge	Hospital patient records/ GP patient records
Neurological function (mRS score) at 30 days and hospital discharge	30 days and hospital discharge	Assessment of patient and/or clinical records by research paramedic/GP to determine mRS score

Table 1: Clinical outcomes

The ultimate aim of cardiac arrest treatment is to achieve survival with good neurological function and this is one of the prioritised outcomes making up the consensus-derived core outcome set for cardiac arrest (COSCA).[28] However, an important component of assessment of treatments for cardiac arrest in which the rhythm is shockable is establishing shock efficacy. Key steps in the pathway following successful defibrillation are shown below:

Figure 2: Pathway to survival following successful defibrillation

VF = ventricular fibrillation pVT = pulsed ventricular tachycardia ROOR = return of organised rhythm ROSC = return of spontaneous circulation

Traditionally, shock success was defined as the ability of a shock to cease the chaotic electrical activity within the heart, which underlies the mechanical state of fibrillation, within five seconds of shock delivery.[29] However, termination of fibrillation (ToF) is not a good measure of shock success since the termination of all electrical activity (i.e. asystole) would be regarded as a successful outcome whereas this is the worst possible clinical outcome. The Return of Spontaneous Circulation (ROSC) would be a preferred patient-focussed outcome but is problematic since it is

difficult to reliably detect in the prehospital setting.[30] ROSC is usually indicated by the manual detection of a carotid pulse. However, when circulation is first re-established the pulse is often weak and healthcare providers have low confidence in their ability to detect weak pulses.[31, 32] In such cases ROSC may be misclassified as Pulseless Electrical Activity (PEA).[33] The in-hospital practice of verifying ROSC using end-tidal carbon dioxide monitoring is not currently routine prehospital practice in the UK.[34] Although possible to confirm ROSC using such monitoring at the time of hospital handover this time point would not provide a pure indicator of shock success due to possible confounding by post-shock treatments.

Return of organised rhythm (ROOR), defined as the detection of two QRS complexes <5s apart, offers a sensitive marker of shock success. Its presence can be assessed by analysis of cardiac rhythm data recorded by defibrillators during guideline-specified pauses in CPR. These pauses occur two minutes post-shock and allow rescuers to analyse a cardiac rhythm in order to determine whether they should deliver a shock. A recent observational study found that these two-minute rhythm checks could provide valuable prognostic information and identified ROOR as the best prognostic marker for survival when compared to VF or asystole.[35] If ROOR is not achieved it may be useful to know the resultant rhythm to assess whether too little (VF/pVT) or too much (asystole) energy may have been delivered and hence which side of the dose-response curve the energy level falls.[36]

The secondary outcomes, survival and neurological function at 30 days, are distal clinical markers of shock success but are the COSCA-recommended outcome measures of resuscitation success.[28] These outcomes can be reported either at discharge or 30 days, in accordance with the Utstein cardiac arrest reporting template, but reporting of a composite outcome (i.e. 'discharge or 30 days') is discouraged. [28, 37] The modified Rankin Scale (mRS) is an adapted version of a scale used to assess level of disability following non-fatal stroke.[38] It is an ordinal scale scoring level of disability from 0 (no symptoms) to 6 (dead) which may be conducted through face to face or telephone interview of the patient or informant.[39] Where this is not possible, trained health professionals may reliably administer the rating through assessment of hospital notes.[39]

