7.4	Notification of serious breaches to GCP and/or study protocol.....	49
7.5	Indemnity.....	49
7.6	Study timetable and milestones.....	50
7.7	Administration.....	50
7.8	Study Management Group (SMG).....	50
7.9	Study Oversight Committee (SOC).....	50
7.10	Data Monitoring Committee (DMC).....	51
7.11	Essential Documentation.....	51
7.12	Financial Support.....	51
8.	MONITORING, AUDIT AND INSPECTION.....	51
9.	PATIENT AND PUBLIC INVOLVEMENT (PPI).....	52
10.	DISSEMINATION AND PUBLICATION.....	53
11.	REFERENCES.....	54

LIST OF TABLES

PAGE

No table of figures entries found.

LIST OF FIGURES

PAGE

Figure 1	Study flow diagram.....	19
Figure 2	Pathway to survival following successful defibrillation.....	22
Figure 3	Strategies for informing participants/relatives.....	26

STUDY SUMMARY

Study Title	A feasibility study of Prehospital Optimal Shock Energy for Defibrillation	
Short title	POSED	
Study Design	Single site three-armed parallel-group feasibility randomised controlled trial	
Study Participants	Adult patients sustaining out-of-hospital cardiac arrest attended by a crew from the participating ambulance service in whom resuscitation is attempted and a shock indicated.	
Planned sample size	90 (30 in each arm)	
Treatment Duration	Duration of cardiac arrest (up to approximately 60-minutes)	
Follow-up Duration	To hospital discharge and 30-days	
Planned Study Period	From Sep 2020 to Nov 2022	
	Objectives	Outcome Measures
Primary	Establish whether it is feasible to conduct a large scale definitive trial by establishing the number of eligible patients and the number recruited.	Eligibility screening logs based on Ambulance Service call data and clinical records.
Secondary	
 To measure the rate of adherence to the allocated treatment. Identify the best outcome measures in terms of ease and reliability of recording by reviewing data completeness 	
Rate of compliance with treatment allocation
 
Rate of shock data capture on clinical records; Rate of Rankin Focussed Assessment (RFA) completion

	Objectives	Outcome Measures
Sub-studies		
Qualitative	Exploration of views and experiences of paramedics regarding recruitment, treatment adherence and data completeness	Analysis of focus groups data

LIST OF ABBREVIATIONS/GLOSSARY

Abbreviation	Explanation
AE	Adverse Event
<hr/>	
AED	Automated External Defibrillator
BTE	Biphasic Truncated Exponential waveform
CAD	Computer Aided Despatch
CCU	Coronary Care Unit
CI	Chief Investigator

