5. DATA MANAGEMENT

A Data Management Plan will be created in accordance with University of Warwick SOPs.

Personal data collected during the study will be handled and stored in accordance with the Data Protection Act 2018 which encompassed the requirements of the EU General Data Protection Regulations and Warwick CTU SOP 15 'Data Management'.

For this feasibility study, participants will be identified using a unique study number only. Personal identifiable data will be shared between the Ambulance service and the receiving hospital for the purpose of follow-up to hospital discharge. Outcome data for those patients missed in hospital will be sought by the Ambulance Service from the patient's GP. Personal identifiable information will therefore be shared between these agencies for this purpose.

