Information requests for patients not known to have died will be sent to the appropriate research team at the destination hospital. Information sought will include patient identifiers that the ambulance staff may have been unable to obtain, including survival status, patient location and date of transfer to the hospital ward. This will be sought by completion of a spreadsheet and will be sent securely via nhs.net email system. Ongoing checks regarding patient location and survival status will be made in order that a visit may be arranged at the appropriate time. Personal identifiers will only be shared between those in the direct care team, i.e. the ambulance service and the destination hospital, and not with the WCTU.

The mRS scores of surviving patients will be assessed at 30-days post event by the research paramedics using the Rankin Focussed Assessment (RFA) tool. This tool has excellent inter-observer reliability (unweighted κ of 0.93 (95% CI, 0.85-1.00)).[47] At 30 days, patients may have been

discharged home or they may be on the hospital ward. We will arrange to visit patients in either location to assess mRS. If the patient has been discharged home, two survival checks will first be made before telephoning the patient. Assessing mRS when they have been discharged into their home setting allows patients to accurately assess their abilities regarding their normal activities.[28] However, since the RFA encourages the gathering of information from all available sources it may also be reliably applied in the hospital setting.[47] Should the patient lack capacity at 30 days and remain in hospital the RFA will be completed with the consultee, nursing staff and the medical notes. Should they be at home, the opinion of the patient's consultee will be sought to complete the RFA. Where a proxy is required for mRS assessment, family members have been found to be more reliable than nurses or therapists.[48] A lone working risk assessment shall be carried out in accordance with the Warwick SOP. Home visits shall be carried out within office hours and within daylight hours where possible. Research paramedics shall ensure that they inform a member of the study team prior to entering an address, carry a mobile phone and undertake a dynamic risk assessment during the visit and inform the study team on leaving the address.

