5.4 Data access and quality assurance

There is no requirement to collect personal information about potential participants. The only details required are call details and an assessment against the eligibility criteria. Information about enrolled participants will be collected by the research paramedics at site. Personal identifiable details will not be required for those patients known to have died. The purpose of gathering personal identifiable data regarding those patients not known to have died is to allow tracking

through hospital and follow up. Data will be gathered from source documents and entered directly onto the study database.

Information regarding patients not known to have died shall be shared between the site study team and the relevant research team in the destination hospital. The minimum data necessary to identify the correct patient and allow follow up shall be shared. This includes full name, date of birth, address, NHS number and GP surgery. Data will be shared between site and the destination on a password-protected spreadsheet via the secure nhs.net system. At the meeting to potentially grant consent, the research paramedic will seek a contact phone number and/or email address for the patient to allow follow up. This will not be necessary if this meeting coincides with the 30-day time point and the patient is still in hospital. Should contact with the patient's GP be required, to acquire outcome data if the patient has left hospital prior to being approached by a research paramedic and has not responded to invitation letters, identifiable information shall be shared with the GP to ensure correct patient identification.

Consent forms shall be securely stored at site with access only available to the site study team. They shall be securely shredded at study closure. Electronic documents shall be stored on the site server in a folder with access restricted to the study team only. Access permissions are granted/revoked by the Trust's IT team to remain secure.

Direct access to source data/documents may be required for study-related monitoring or audit by WCTU.

An electronic copy of the final study data set shall be sent to the participating ambulance service on completion of the study.

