6.2.3.3 Secondary outcome analysis

The secondary outcomes that will be assessed are:

- Treatment adherence rate. This will be assessed in terms of how many patients received the allocated first shock energy and, where more than one shock was delivered, how many received the correct subsequent shock energies.
- Data completeness of clinical outcomes below:
 - Neurologically intact survival at 30 days and hospital discharge (mRS score)
 - Return Of Organised Rhythm (ROOR) 2 min post shock

- Resulting rhythm (VF/pVT/PEA/asystole) 2 min post shock
- Re-arrest rate (re-fibrillation)
- Survived event (return of spontaneous circulation (ROSC) at hospital handover)
- Survived to hospital discharge and 30 days

These will be reported in terms of the proportion of patients for whom each of these outcomes was collected.

- Data completeness of process outcomes below:
 - Quality of CPR (chest compression rate, chest compression depth, chest compression fraction, pre-shock pause, post-shock pause)
 - Number of shocks
 - Advanced airway applied (% advanced airway applied and % supraglottic airway or endotracheal tube)
 - Intravenous medicines administered (% cases where medicines administered and % adrenaline, amiodarone)
 - Transported to hospital (% transported)
- Issues identified by ambulance staff and suggestions for study optimisation. These will be reported in terms of the topics identified, with example anonymised quotes, from the thematic analysis of the focus group data.
- Acceptability of approach to informing relatives of non-survivors. We will monitor the number and nature of enquiries received by the Ambulance Service, the time taken to identify next of kin, the sources consulted to verify next of kin details and the concordance/discordance between different sources.

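### The Study Summary declares RFA completion as the measure, but 6.2.3.3 reports only whether an mRS was collected, so a GP-derived or notes-only score without the RFA would count as complete

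*Protocol*

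**What the plan says.** The Study Summary lists, as an outcome measure for the data-completeness objective, the "Rate of Rankin Focussed Assessment (RFA) completion".

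Section 5.1 names the rater and the tool: "The mRS scores of surviving patients will be assessed at 30-days post event by the research paramedics using the Rankin Focussed Assessment (RFA) tool". It supports the choice with "This tool has excellent inter-observer reliability" and cites an unweighted kappa of 0.93 (95% CI 0.85 to 1.00). It also lets the RFA draw on several sources. For a patient without capacity who is still in hospital, these are the consultee, the nursing staff and the medical notes.

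Table 1 in section 2.3.2 gives the mRS source as "Assessment of patient and/or clinical records by research paramedic/GP to determine mRS score". The RFA is not mentioned there. The text of 2.3.2 adds that, where interview is not possible, "trained health professionals may reliably administer the rating through assessment of hospital notes".

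Section 5 states: "Outcome data for those patients missed in hospital will be sought by the Ambulance Service from the patient's GP". Section 5.4 describes GP contact "to acquire outcome data if the patient has left hospital prior to being approached by a research paramedic" where the patient has also not replied to invitation letters.

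For the clinical outcomes, including the mRS, section 6.2.3.3 says: "These will be reported in terms of the proportion of patients for whom each of these outcomes was collected". The RFA does not appear in section 6.

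**The concern.** One of the secondary objectives (2.2.2) is to identify outcome measures that can be recorded easily and reliably, judged by data completeness. For neurological outcome the Summary makes that operational as RFA completion. The analysis section replaces it with a wider count that accepts any mRS from any rater by any method.

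The two counts differ whenever a survivor has an mRS but no RFA. Table 1 provides for this by naming the GP, because the protocol assigns the RFA to research paramedics and nowhere says that a GP would use it. The pooled count cannot show whether the intended instrument was feasible. Anyone planning the definitive trial could read a high mRS completeness figure as support for the RFA, although the reliability quoted in 5.1 is that of the RFA and does not cover a score made without it.

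**Working it through.** **Figure to reproduce.** The protocol states no expected rate for mRS or RFA completeness. The only related figure, 90 patients as 3 x 30, is consistent.

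**The statements side by side**

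| Place | What is counted or accepted | Rater | Tool |
|---|---|---|---|
| Study Summary | RFA completed | not stated | RFA |
| 5.1 | mRS of survivors at 30 days | research paramedic | RFA |
| 2.3.2, Table 1 | mRS from patient and/or clinical records | research paramedic or GP | not stated |
| 2.3.2, text | mRS from hospital notes if interview is not possible | trained health professional | not stated |
| 6.2.3.3 | mRS collected, as a proportion of patients | any | any |

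**How each kind of score is counted**

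- Research paramedic, RFA with patient or proxy: counts under the Summary and under 6.2.3.3.
- Research paramedic, RFA informed by records: counts under both, because 5.1 lets the RFA use notes.
- Notes-only rating without the RFA: counts under 6.2.3.3 only.
- GP-derived mRS: counts under 6.2.3.3 only, since no RFA by a GP is described.

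The mismatch therefore lies in the last two rows, not in every use of records.

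**Size per case**

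Inputs: sample size 90 (6.1); survival to discharge 20.9% for initially shockable rhythms (1.1), used as an assumption.

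- Survivors: 90 x 0.209 = 18.8, about 19.
- Gap per survivor scored without an RFA: 1/19 = 5.3 percentage points. With one such case and all survivors otherwise rated, mRS collected is 19/19 = 100% and RFA completed is 18/19 = 94.7%.
- Assumed survival of 15%: 90 x 0.15 = 13.5, taken as 14; gap 1/14 = 7.1 points.
- Assumed survival of 30%: 90 x 0.30 = 27; gap 1/27 = 3.7 points.

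The range is needed because 2.1 also admits patients whose shockable rhythm came later, to whom the 20.9% need not apply.

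**Denominator**

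Section 6.2.3.3 speaks of patients, not survivors. The mRS runs to 6 for death (2.3.2), and the protocol does not say whether deaths count as collected scores.

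- Over all 90 patients, one score without an RFA is 1/90 = 1.1 points, so the gap almost disappears from view.
- If deaths do count, 90 - 19 = 71 deaths would give 71/90 = 79% completeness before any survivor had been rated.

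The RFA question concerns survivors only, so the denominator should be patients alive at the time point.

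**The case against.** The strongest reply is that these are two measures rather than a contradiction. RFA completion and mRS collected can both be reported, and 5.1 keeps the paper RFA sheets at site, so an RFA count could be recovered. That is fair. It does not settle the point, because section 6 analyses only one of the two, and it is not the one that the Summary declares.

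A second reply is that display is left to the SAP (6.2.3). A source breakdown could indeed go there. But 6.2.3.3 already fixes how completeness will be reported, and the mismatch is within the protocol.

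Three stronger readings are tempting and lack support.

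- A reader might infer that every score from records bypasses the RFA. Section 5.1 says otherwise.
- A reader might infer that many survivors would be scored by a GP. No frequency is given, and 2.7.6 treats failure to make contact in hospital as exceptional. Sections 5 and 5.4 speak of outcome data without naming the mRS, and Table 1 separately lists GP records as a source for survival. Section 1.5.7 ties GP follow-up to consent, and 3.2 limits mRS assessment to willing patients, so someone who never answered a letter may contribute survival status only. That a GP supplies an mRS at all rests on the mRS row of Table 1.
- A reader might infer that patients reached through the GP left hospital early and so function better, which would bias the scores. No figure or statement supports this. No formal comparison between arms is planned either (6.2.1).

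**Conclusion.** The point holds in a limited form. The measure declared in the Summary is not analysed in 6.2.3.3, and the count used there accepts mRS scores from a GP, or from notes without the RFA, as complete. It also does not restrict the denominator to survivors.

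The mismatch follows from the wording alone and needs no numerical assumption. Its size cannot be stated, because the protocol does not say how often such scores would arise. Per case it is about 5 points with about 19 survivors, or 7.1 to 3.7 points for assumed survival of 15% to 30%. The 20.9% is a discharge figure for initially shockable rhythms and serves only as an illustration. The documents do not support a claim that the total gap would be large, or that the affected patients differ in function.

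**What to change.** In 6.2.3.3, with patients alive at the time point as the denominator, report:

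1. the RFA completion rate, with patient or proxy, as the measure named in the Summary;
2. separately, mRS obtained only from a GP or from notes without the RFA;
3. mRS not obtained.

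Add a CRF field for the source and tool of each rating. Reconcile Table 1 with 5.1 by stating whether the GP supplies an mRS or only survival status and, if an mRS, by what method.

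The cost is one CRF field, a few table rows and a wording change in Table 1 and 6.2.3.3. No visit, assessment or patient contact is added.

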2.3.3 Process outcomes

Process outcomes, including CPR metrics and resuscitation treatments, will be reported. These will be obtained from the defibrillator data downloads and electronic patient record. The following process outcomes will be recorded:

- Quality of CPR (chest compression rate, chest compression depth, chest compression fraction, pre-shock pause, post-shock pause)

- Number of shocks
- Advanced airway applied (% advanced airway applied and % supraglottic airway or endotracheal tube)
- Intravenous medicines administered (% cases where medicines administered and % adrenaline, amiodarone)
- Transported to hospital (% transported)

2.3.4 Safety

In addition to the reporting of outcomes, the system for reporting adverse events and serious adverse events by ambulance service staff will follow the WCTU SOP (see section 4).

2.4 Eligibility criteria

Patients are eligible to be included in the study if they meet the following criteria:

2.4.1 Inclusion criteria

1. Patients sustaining OHCA attended by a crew from participating ambulance service
2. Resuscitation attempted and shock delivered as per Resuscitation Council UK and JRCALC guidelines

2.4.2 Exclusion criteria

1. Patients known or suspected to be under 18 years old

Since the study is not powered to answer a clinical question about this specific group, we consider that the burden of follow-up to these patients and/or family would outweigh any potential benefits and so they will be excluded from the study.

Existing resuscitation protocol advises an initial shock energy of 150J, or to follow manufacturer's guidance.[6] The study protocol is therefore consistent with existing resuscitation protocols.

